4.2 Non-investigational Product

Other medications used as support or escape medication for preventative, diagnostic, or therapeutic reasons, as components of the standard of care for a given diagnosis, may be considered as non-*IPs*. In this study, corticosteroids are considered non-*IP* and will not be provided by the Sponsor.

4.3 Storage and Dispensing

The product storage manager should ensure that the study drug is stored in accordance with the environmental conditions (temperature, light, and humidity) as determined by Roche. If concerns regarding the quality or appearance of the study drug arise, the study drug should not be dispensed and contact Roche immediately.

Study drug not supplied by Roche will be stored in accordance with the package insert.

IP documentation (whether supplied by Roche or not) must be maintained that includes all processes required to ensure drug is accurately administered. This includes documentation of drug storage, administration and, as applicable, storage temperatures, reconstitution, and use of required processes (e.g., required diluents, administration sets).

Parents/caregivers must be instructed by the site staff to bring used containers of study drug to each study visit; this will allow site staff to assess study drug accountability. Study drug must be transported to and from the site in a cooler with an ice pack to maintain the appropriate storage temperature. If approved by the local IRB/EC, the cooler and ice pack for study drug transport will be provided by the Sponsor.

Parents/caregivers must be instructed by the site staff on Sharps handling procedures. Parents/caregivers should be instructed to return the Sharps container to the study site for proper disposal.

4.4 Method of Assigning Subject Identification

Within each panel, subjects will be randomized to receive either RO7239361 or placebo according to a computer-generated randomization scheme.

During the screening visit, the investigative site will enter into the enrollment option of the interactive web response system (IWRS) designated by Roche for assignment of a 5-digit subject number that will be unique across all sites. Enrolled subjects, including those not dosed, will be assigned sequential subject numbers starting with 00001 (e.g., 00001, 00002, 00003.... 00010). The patient identification number (PID) will ultimately be comprised of the site number and subject number. For example, the first subject screened (i.e., enrolled) at site number 1, will have a PID of 0001 00001. Once it is determined that the subject meets the eligibility criteria following the screening visit, the investigative site will enter into the IWRS to randomize the subject into the open-dose panel.

Subjects will not be replaced if they are discontinued from the study secondary to an *AE* unless the *AE* can be determined to be unrelated to treatment. Subjects may be replaced if corticosteroid use is discontinued while on treatment. If a subject is replaced after dosing, then the replacement subject will be assigned the original subject's number plus 100. The replacement subject will receive the same treatment as the subject being replaced but a new randomization number will be assigned to him. For example, Subject 00004 would be replaced by Subject 00104.

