3.5 Discontinuation of Subjects following any Treatment with Study Drug

Subjects MUST discontinue investigational product (and non-investigational product at the discretion of the investigator) for any of the following reasons:

- Subject's request to stop study treatment and/or participation in the study
- Any clinical AE, laboratory abnormality or intercurrent illness which, in the opinion of the investigator, indicates that continued participation in the study is not in the best interest of the subject
- Termination of the study by Roche
- Loss of the ability of the parent/legal guardian to freely provide consent through imprisonment or involuntarily incarceration for treatment of either a psychiatric or physical (e.g., infectious disease) illness
- Unblinding a subject for any reason (emergency or non-emergency)
- Inability to comply with protocol
- Discretion of the investigator

Clinical Criteria for Stopping Dose Escalation or Dose Discontinuation:

- Dose escalation will be halted and dosing within a dose panel may be stopped until safety information can be reviewed in the event that:
 - Two (2) or more subjects experience the same severe or very severe adverse event that is considered related to RO7239361, or;
 - Two (2) or more subjects show a decrease in ejection fraction to less than 50% (confirmed by repeat echocardiogram) that is considered related to RO7239361
- Dosing will be paused within a subject until safety information is reviewed and drug-induced liver injury (DILI) is ruled out in the event that:
 - ALT > 5 x baseline AND no corresponding increase in CPK to indicate muscle origin as the reason for the increase in ALT

OR

- ALT > 10 x ULN AND ALT > 2 x baseline AND no corresponding increase in CPK to indicate muscle origin as the reason for the increase in ALT

OR

- Total bilirubin > 2 x ULN

OR

- Symptoms or signs of hepatic inflammation such as nausea, vomiting, right upper quadrant pain, or tenderness with no other immediately apparent possible cause of these symptoms or signs, such as viral gastroenteritis or constipation.

In addition to the above stopping rules, dosing may be paused or halted for a subject or a panel if a review of safety and tolerability data, or the clinical judgment of the investigator, suggest the emergence of a new potentially serious safety signal, including DILI.

The following categories and definitions of intensity as determined by a physician should be

used *assessing the severity of AEs*:

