8 STATISTICAL CONSIDERATIONS

8.1 Sample Size Determination

The total number of subjects of the study will be approximately 40, which consists of 3 dose panels of approximately 8 subjects each and an Expansion Panel of approximately 16 subjects. In each dose panel, subjects will be randomized 3:1 to either RO7239361 or placebo. Subjects who discontinue participation in the study prematurely may be replaced only if the reason for discontinuation is not related to study drug. For safety evaluation, the administration of RO7239361 to 6 subjects provides an 80% probability of observing at least one occurrence of any adverse event that would occur with 24% incidence in the population from which the sample is drawn.

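### A replacement boy inherits the arm and a linked number of the boy he replaces, with no exception when that boy was unblinded, so site staff can know his arm from Day 1

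*Combined protocol and SAP*

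**What the plan says.** Section 4.4 of the protocol fixes a replacement's arm: "The replacement subject will receive the same treatment as the subject being replaced but a new randomization number will be assigned to him". It also fixes his subject number: "If a subject is replaced after dosing, then the replacement subject will be assigned the original subject's number plus 100". The example given is explicit: "For example, Subject 00004 would be replaced by Subject 00104".

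Eligibility for replacement is set in two places. Section 4.4 says: "Subjects will not be replaced if they are discontinued from the study secondary to an *AE* unless the *AE* can be determined to be unrelated". Section 8.1 says that subjects who leave early "may be replaced only if the reason for discontinuation is not related to study drug".

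Section 3.5 lists the reasons for which study drug must be stopped. One of them is "Unblinding a subject for any reason (emergency or non-emergency".

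Section 4.6 lets the investigator break the blind in an emergency through the response system without asking the sponsor first. It also covers accidental unblinding and non-emergency requests. Otherwise, sites learn the allocations only with the final study report.

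**The concern.** Each rule is reasonable alone. Together they give a path by which a boy enters the double-blind phase with his arm already known at the site. The new randomization number does not protect him, because the same-arm rule and the numbering rule are both printed in the protocol that sites hold.

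The primary endpoint is safety and tolerability. Whether an adverse event is related, and how severe it is, is a physician's judgement. The timed function tests, 6MWD, NSAA and pulmonary function tests depend on effort or on the rater, and PODCI is reported by a parent. A boy whose arm is known to the people assessing him is open to biased reporting and scoring for up to 24 weeks. The groups are small, so one such boy has visible weight.

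**Working it through.** **Inputs.** Section 8.1 gives 3:1 allocation, three panels of about 8, an Expansion Panel of about 16, and about 40 in total. Section 8.2 pools placebo subjects across panels.

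**The plan's own figure.** Section 8.1 states an 80% probability of seeing at least one event of 24% incidence among 6 treated subjects. Check: 1 − (1 − 0.24)^6 = 1 − 0.76^6 = 0.807, so it reproduces. The point does not depend on this figure. It is used below to price one possible remedy.

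**The chain of rules.**
1. The first boy's arm becomes known at his site, by emergency, accidental or non-emergency unblinding (Section 4.6).
2. He must stop study drug (Section 3.5).
3. He may be replaced if the reason is not drug-related (Sections 4.4 and 8.1). That can include an emergency whose adverse event is judged unrelated. It can also include accidental or non-emergency unblinding, where the unblinding itself forces the stop.
4. His replacement gets the same arm and, if the first boy was dosed, his number plus 100: 00004 + 100 = 00104 (Section 4.4).
5. Sections 3.5, 4.4, 4.6 and 8.1 contain nothing that breaks the chain. None excludes unblinded boys from replacement, requires a different site, hides the number link, or re-randomises the replacement.

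**What the site learns.** Under fresh 3:1 allocation, the best guess is active, which is right with probability 3/4 = 75%. Under Section 4.4, a person who knows the first boy's arm and sees the link is right with probability 100%.

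**Weight of one such boy.**
- Escalation panel: 8 × 3/4 = 6 active and 2 placebo. One active boy is 1/6 = 17%.
- Expansion Panel: 16 × 3/4 = 12 active and 4 placebo. One active boy is 1/12 = 8%.
- Pooled placebo: 2 + 2 + 2 + 4 = 10. One placebo boy is 1/10 = 10%.

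These are shares per event. The documents give neither a replacement rate nor an unblinding rate, so no expected number can be computed.

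**Price of dropping arm-matching for everyone.** A replaced active boy would have a 25% chance of a placebo replacement. Counting completers only, that leaves 5 active boys in an escalation panel, and the Section 8.1 probability becomes 1 − 0.76^5 = 0.746, or 75% against 81%. A replaced placebo boy would have a 75% chance of an active replacement, leaving one placebo completer in that panel. Arm-matching therefore has value while the first boy's arm is undisclosed.

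**The case against.** The strongest reply is that the path is narrow. Section 4.6 discourages unblinding when an emergency is clearly unrelated to the product, and reserves it for cases where it would change immediate management. Section 4.4 bars replacement after an adverse event unless that event is unrelated. Both conditions must therefore hold on the adverse-event route. This stands for that route. It does not close accidental or non-emergency unblinding, which also forces a stop without a drug-related reason.

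Second, replacement is optional, the plus-100 number applies only after dosing, and the study is multi-site. At another site, the staff who know the first boy's arm may never assess the replacement. This stands as a limit on how often the problem can arise.

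Third, function tests and PODCI are exploratory, interim analyses involve no formal inference, and echocardiograms, ECGs and laboratory tests are read centrally. That limits the damage, but leaves adverse-event causality and severity exposed.

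Several stronger readings are tempting but unsupported:
- **The Medical Monitor learns the arm.** Section 4.6 requires that the Medical Monitor and/or study director be told of the unblinding. It does not say that the allocation is passed on.
- **Unblinded sponsor staff gain new knowledge.** Section 4.6 already lets designated staff be unblinded at any time, so the link tells them nothing they could not see.
- **The site knows the arm before choosing whom to enrol.** This needs a same-site replacement and a link visible before randomisation. Section 4.4 assigns subject numbers at screening, but does not say when the plus-100 number is given or that a site knows which boy fills the slot.
- **One placebo boy is half of a panel's placebo group.** Placebo is analysed as one pooled group, so 1/10 is the relevant share.
- **The corticosteroid rule contradicts Section 8.1.** Section 4.4 says "Subjects may be replaced if corticosteroid use is discontinued while on treatment", with no relatedness test. A permission there and a general limit in Section 8.1 can be read together, and the catch-all reasons in Section 3.5 can cover a steroid stop.

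**Conclusion.** The concern holds as a missing safeguard. Followed as written, the protocol allows a replacement whose arm is certain to any site staff who know the first boy's allocation and see the linked number, instead of a 75% best guess. The conclusion rests on three conditions: the first boy's arm has been disclosed at a site, he is replaced, and staff with that knowledge assess the replacement. The documents permit all three together and require none of them.

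The event is probably rare. If it occurs, one boy is 17% of an escalation panel's active group, 8% of the Expansion Panel's active group, or 10% of pooled placebo. No sample size or stated probability in the plan changes. Same-arm replacement has a sound purpose, which is to keep the 6:2 split; the fault is that it has no exception for a disclosed allocation.

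**What to change.** In Section 4.4:
1. Keep same-arm replacement only while the original subject's allocation is undisclosed outside the designated unblinded team. If it has been disclosed, have the IWRS randomise the replacement from the next unused entry on the panel's list or from a reserve block.
2. Give every replacement an ordinary sequential subject number, with the link to the original held only by the IWRS or the unblinded team.

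Both parts are needed. Hiding the number alone would not help a site that can guess that its next boy fills the vacancy.

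The cost is a few protocol sentences and an IWRS setting. In the rare cases where the replacement is randomised, an escalation panel's 6:2 split may shift by one boy per such replacement.

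Version 6 mainly concerns the open-label extension, and Section 1.1 already reports interim results, so double-blind enrolment may be complete. That is an inference; the documents do not state it. If it is complete, the study report should say how many replacements followed an unblinded subject and show the key double-blind summaries without them.

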4.5 Selection and Timing of Dose for Each Subject

The levels of free myostatin at Week 5 in Study CN001001 of normal healthy volunteers were used to determine the dose ranges for the present study. The lowest dose in this study (Panel 1 dose; see [Table 4.5-1](#)) is a dose that targets achievement of >50% suppression in levels of free myostatin at trough after 5 weeks of weekly dosing and is lower than the starting weekly dose of that study of normal healthy volunteers that produced approximately 83% reduction in free myostatin at trough at Week 5. The dose for Panel 1 has a safety margin in children in the weight range anticipated for subjects in this study²¹ of 15 kg to 70 kg of about 232x relative to the Week 12 exposures in the juvenile rat toxicity study.

Table 4.5-1: Panel 1 Dose

Body Weight Tier	Fixed Dose (mg) /Volume (mL)
≥ 15 kg	4.0 mg /0.08 mL

The middle dose in this study (Panel 2 dose; [Table 4.5-2](#)) is a dose that targets achievement of > 85% suppression in levels of free myostatin at trough after 5 weeks of weekly dosing. The dose for Panel 2 has a safety margin in children in the weight range of 15 kg to 70 kg of about 45x, relative to the Week 12 exposures in the juvenile rat toxicity study.

Table 4.5-2: **Panel 2 Dose**

Body Weight Tier	Fixed Dose (mg)/Volume (mL)
≥ 15 kg to ≤ 45 kg	12.5 mg/0.25 mL
> 45 kg	20.0 mg/0.4 mL

The highest dose in this study (Panel 3; [Table 4.5-3](#)) is a dose that targets achievement of > 95% suppression in levels of free myostatin at trough after 5 weeks of weekly dosing. The dose for Panel 3 has a safety margin in children in the weight range of 15 kg to 70 kg of about 16x relative to the Week 12 exposures in the juvenile rat toxicity study. A review of safety data from Panels 1–3 supports the selection of the Panel 3 dose (35 mg for subjects ≥ 15 kg to ≥ 45 kg; 50 mg for subjects > 45 kg) for the Expansion panel.

Table 4.5-3: **Panel 3 Dose**

Body Weight Tier	Fixed Dose (mg)/Volume (mL)
≥ 15 kg to ≤ 45 kg	35.0 mg/0.7 mL
> 45 kg	50.0 mg/1 mL

Table 4.5-4: **Expansion Panel Dose**

Body Weight Tier	Fixed Dose (mg) /Volume (mL)
≥ 15 kg to ≤ 45 kg	35.0 mg/0.7 mL
> 45 kg	50.0 mg/1 mL

Subjects will receive SC doses of RO7239361/placebo weekly. During Part A (first four weeks of Panels 1–3), study drug should be administered every 7 days. During Part B of the double-blind phase (Weeks 5–24 of Panels 1–3 and Expansion Panel) and during the 48-week OL phase, the study drug should be administered every 7 days within a ±1-day window.

Subjects may receive the weekly dose at home, starting on Day 22. If the parent/caregiver has been trained by study site staff and is comfortable administering study drug to the subject, the parent/caregiver will receive an adequate supply of study drug in vial (either RO7239361 or placebo during the double-blind phase and RO7239361 in the OL and OLE phases) and sterile syringes for weekly administration at home to their child in between study visits. The first three weekly doses in the OL phase must be administered at the study site, *as well as the first two PFS doses in the OLE phase*.

In Panels 2 and 3, during the first four weeks of dosing (Days 1–29) the dose of RO7239361 should not be adjusted based on weight. Starting at Week 5, subjects whose weight exceeds or drops below the dosing weight tier to which they were assigned by >1 kg should be assigned to the new weight-based dose in the subject's assigned dose panel.

4.6 Blinding/Unblinding

Blinding of treatment assignment is critical to the integrity of this clinical study. However, in the event of a medical emergency in an individual subject in which knowledge of the investigational product is critical to the subject's management, the blind for that subject may be broken by the investigator. The subject's safety takes priority over any other considerations in determining if a treatment assignment should be unblinded.

Before breaking the blind of an individual subject's treatment, the investigator should determine that the unblinded information is necessary (i.e., that it will alter the subject's immediate management). In many cases, particularly when the emergency is clearly not related to the investigational product, the problem may be properly managed by assuming that the subject is receiving active product. It is highly desirable that the decision to unblind treatment assignment be discussed with the medical monitor, but the investigator always has ultimate authority for the decision to unblind. The Principal Investigator should only call in for emergency unblinding AFTER the decision to discontinue the subject has been made.

In cases of accidental unblinding, contact the medical monitor and ensure every attempt is made to preserve the blind.

Any request to unblind a subject for non-emergency purposes should be discussed with the Medical Monitor.

In case of an emergency, the investigator(s) has unrestricted access to randomization information via the interactive voice response system (IVRS) and is capable of breaking the blind through the IVRS without prior approval from the Sponsor. Following the unblinding, the investigator shall notify the Medical Monitor and/or study director.

Further considerations about unblinding are discussed below. Because data emerging from each panel of Part A might be needed for timely decisions about adjustments to procedures in subsequent panels, including early termination of the study, data from these panels can be unblinded after documented completion and review of the corresponding CRFs, prior to the formal locking of the study database. Also, designated staff of Roche can be unblinded at any time. The Bioanalytical Sciences section or its designate will be unblinded to the randomized treatment assignments in order to minimize unnecessary analysis of samples from control group subjects. A pharmacokineticist(s) or designate in Clinical Pharmacology and Pharmacometrics, a biostatistician(s) and programmer(s) in Global Biometric Sciences may be unblinded in order to prepare preliminary summaries of PK, PD, and safety data, as needed before data is more generally unblinded. Additionally, data from subjects can be unblinded for *IA*s that are discussed in [Section 8.5](#). Except for the *IA*, including all data from the double-blind period, summaries for these analyses will not reveal individual subjects' treatment assignments. Except as noted above, other members of Roche will remain blinded. Target

engagement and immunogenicity results from subjects will be masked to site, subject and Roche personnel, excluding the pharmacokineticist or designate, biostatistician and programmer as referenced above.

The randomization assignments will be released to the study sites by the final study report generated for the study.

4.7 Treatment Compliance

Study drug will be administered in the clinical facility or off-site by the parent/caregiver. The parent/caregiver may administer study drug on or after the Day 22 dose and once trained and comfortable with SC injections of study drug/placebo. For any dose administered at the clinical facility, the dose and location of each SC injection must be recorded in the source record.

For any dose administered off-site (off-site dosing is allowed starting on Day 22) of double-blind phase and at Week 4 of the open label phase), the parents/caregivers must be instructed on proper administration of study drug. The site staff must also instruct the parents/caregivers to bring used and/or empty vials to each study visit. The subjects and parents/caregivers will be provided with a dosing diary to record administration of study drug and be instructed to record the location and dose of each SC injection. Parents/caregivers must be instructed to bring the used and/or empty vials and the dosing diary to each study visit; this will allow site staff to assess treatment compliance and study drug accountability. A dosing diary will also be provided to the parent/caregiver to record the subject's corticosteroid therapy. Study drug must be transported to and from the site in a cooler with an ice pack to maintain the appropriate storage temperature. If approved by the local IRB/EC, the cooler and ice pack for study drug transport will be provided by the Sponsor.

Parents/caregivers must be instructed by the site staff on Sharps handling procedures. Parents/caregivers should be instructed to return the sharps container to the study site for proper disposal.

4.8 Destruction of Study Drug

For this study, study drugs (those supplied by Roche or sourced by the investigator) such as partially used study drug containers, vials and syringes may be destroyed on site.

Any unused study drugs can only be destroyed after being inspected and reconciled by the responsible Roche study monitor unless study drug containers must be immediately destroyed as required for safety, or to meet local regulations (e.g., cytotoxics or biologics).

On-site destruction is allowed provided the following minimal standards are met:

- On-site disposal practices must not expose humans to risks from the drug.
- On-site disposal practices and procedures are in agreement with applicable laws and regulations, including any special requirements for controlled or hazardous substances.
- Written procedures for on-site disposal are available and followed. The procedures must be filed with the site's SOPs and a copy provided to Roche upon request.
- Records are maintained that allow for traceability of each container, including the date disposed of, quantity disposed, and identification of the person disposing the containers. The

method of disposal (i.e., incinerator, licensed sanitary landfill, or licensed waste disposal vendor) must be documented.

- Accountability and disposal records are complete, up-to-date, and available for the monitor to review throughout the clinical trial period.

If conditions for destruction cannot be met the responsible Roche study monitor will make arrangements for return of study drug.

It is the investigator's responsibility to arrange for disposal of all empty containers, provided that procedures for proper disposal have been established according to applicable federal, state, local, and institutional guidelines and procedures, and provided that appropriate records of disposal are kept.

